8.6. Analysis of the Primary Efficacy Endpoint

Table 4:	Summary (of Analyses	Related to the	Primary Effic	cacy Endpoint
	•	•		•/	•

Analysis	Population	Handling of Intercurrent Events	Analysis Approach
Primary Analysis: All- cause hospitalizations and deaths (through Day 29)	mITT-S	Treatment policy	Cochran-Mantel-Haenszel
Supplemental Analysis: All-cause hospitalizations and deaths (through Day 29)	mITT-S Completers	Treatment policy	Cochran-Mantel-Haenszel
Supplemental Analysis: All-cause hospitalizations and deaths (through Day 29)	mITT-S Per-protocol	Treatment policy	Cochran-Mantel-Haenszel
Supplemental Analysis: All cause hospitalizations and deaths (through Day 29)	mITT-S	Intervention with COVID-19 rescue as event (composite handling); Treatment policy otherwise	Cochran-Mantel-Haenszel
Supplemental Analysis: Time to all cause hospitalization and death (through Day 29)	mITT-S	Intervention with COVID-19 rescue as event (composite handling); Treatment policy with censoring for early study discontinuation (prior to Day 29) without event	Kaplan-Meier plot, stratified logrank test

8.6.1. Primary Efficacy Analysis

The primary efficacy objective of this study is to evaluate the efficacy of BEM based on the proportion of subjects who are hospitalized for any cause or who died due to any cause through Day 29 in the supportive-care-only population. Hospitalization is defined as >24 hours of acute care, in a hospital or similar acute care facility, including Emergency Rooms or temporary facilities instituted to address medical needs of those with severe COVID-19 during the COVID-19 pandemic. This includes specialized acute medical care unit within an assisted living facility

or nursing home. This does not include hospitalization for the purposes of public health and/or clinical trial execution. Furthermore, scheduled hospitalization for a pre-planned procedure (including chemotherapy) to treat a pre-existing condition that has not worsened is not an SAE, and would not be considered a hospitalization for the purposes of the efficacy analyses. A pre-existing condition is a clinical condition that is diagnosed prior to the use of study drug and is documented in the subject's medical history.

The primary estimand is the difference in the proportions of subjects who are hospitalized for any cause or who died due to any cause through Day 29 in the supportive-care-only population, and the primary treatment effect comparison will be between the BEM arm and the placebo arm. This proportion will be compared between the BEM and placebo arms using a CMH test adjusted for the stratification factors of age and region. The CMH p-value and estimated common risk difference, odds ratio and relative risk, along with the corresponding 95% confidence intervals (CIs) for these estimates, will be presented. The confidence interval for the common risk difference will be computed using the Klingenberg method⁵. Summary tables will include tabulation of the number of events, by type of event (hospitalization, death).

The analysis will be carried out using the following sample SAS code:

Each region-age combined strata has a 2×2 table with counts for BEM hospitalized, BEM not hospitalized, Placebo hospitalized, and Placebo not hospitalized. In total there will be 8 strata. When low number of events happens and the model can't be carried out, removal of strata will be carried out in the following order: age first, then region. If all strata are indicated to be removed, then an unstratified comparison will be carried out.

Intercurrent events are those that occur after treatment initiation and either preclude observation of the variable or affect its interpretation. For the intercurrent events of rescue (e.g., intervention with remdesivir; these will be identified by blinded medical review prior to analysis), a treatment policy approach will be taken, whereby use of rescue and concomitant medications will be ignored, and observations collected after they are administered to the subject will be used. In addition, subjects will be followed, assessed, and analyzed irrespective of their completion of the course of the study treatment. The analysis will be performed based on observed data, and the following measures will be used to reduce missing hospitalization/death data:

- eCRFs capturing clinical information that may be indicative of hospitalization will be reviewed to mitigate the risk of unreported hospitalizations
- study staff may use a public information source to obtain information about survival status if a patient withdraws from the study.

8.6.2. Sensitivity Analyses of the Primary Efficacy Results

Planned supplemental analyses to support the primary endpoint result are identified in Table 4. The supplemental analyses investigate the impact of significant COVID-19 rescue therapy and data handling for early study discontinuations. For the CMH and stratified log-rank analyses, incorporation of strata will be the same as that used for the primary analysis. The Kaplan-Meier and log-rank analyses will include all data to Day 29.

The primary endpoint may also be analyzed for each of the subgroups defined in Section 8.4 .

8.7. Analysis of the Secondary Efficacy Endpoints

The following secondary endpoints will be analyzed using the same approach as that for the primary endpoint:

- Proportion of subjects in the supportive-care-only population with all-cause hospitalization or all-cause death through Day 60
- Proportion of subjects in the supportive-care-only population with all-cause hospitalization, all-cause death, or COVID-19 related medically attended visits through Day 29 and Day 60.
- Proportion of subjects in the supportive-care-only population with COVID-19-related hospitalization or who died due to any cause death through Day 29 and Day 60
- Proportion of subjects in the supportive-care-only population who died due to any cause through Day 29 and Day 60
- Proportion of subjects in the supportive-care-only population with COVID-19-related complications (e.g., death, hospitalization, radiologically confirmed pneumonia, acute respiratory failure, sepsis, coagulopathy, pericarditis/myocarditis, cardiac failure) through Day 29 and Day 60
- Proportion of subjects in the supportive-care-only population with COVID-19-related medically attended visits (hospitalization, ER visit, urgent care or physician's office visit or telemedicine visit) or who died due to any cause through Day 29 and Day 60.
- Proportion of subjects in the supportive-care-only population with COVID-19-related medically attended visits through Day 29 and Day 60
- Proportion of subjects in the supportive-care-only population with COVID-19 symptom relapse through Day 29
- Proportion of subjects in the supportive-care-only population with viral load rebound through Day 29
- Proportion of subjects in the combination-antiviral population with COVID-19 symptom relapse through Day 29
- Proportion of subjects in the combination-antiviral population with viral load rebound through Day 29

COVID-19 related complications will be adjudicated by blinded medical review prior to analysis.

The proportion of subjects with COVID-19 symptom relapse in each population through Day 29 will be tabulated. This summary will be based on the response to "Have your COVID-19 symptoms returned after previously improving?" (i.e., question 4 in the Symptom Diary, see Section 11.1).

The proportion of subjects with viral load rebound through Day 29 will be tabulated. Viral load rebound is defined as $a \ge 1 \log_{10}$ increase in viral load (measured by RT-qPCR) at any non-missing time point (including unscheduled assessments) after EOT. Subjects must have at least one post-EOT measurement result to be evaluated for viral load rebound.

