^d Safety laboratory tests may be performed at local laboratories if deemed medically necessary by the investigator or Sponsor. In these cases, the site should collect a matching sample and ship it to the central laboratory.

 $^{^{\}mathrm{e}}\mathrm{A}$ documented historical positive result from a test conducted ≤ 5 days prior to randomization is acceptable.

^fNasopharyngeal swabs should be taken at each visit. Should the subject decline a nasopharyngeal swab, a nasal swab may be collected instead. Collection instructions will be provided by the central lab. In addition to SARS-CoV-2 RT-qPCR and resistance, aliquots may be analyzed for viral titer and other respiratory pathogens such as influenza and RSV to rule out co-infection. For subjects with COVID-19 symptom relapse, NP swabs should also be collected at the time of relapse (see Section 6.6)

^hStudy drug dosing should occur on the same day as randomization.

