6.6. Other Laboratory Evaluations

At screening, a RT-PCR or validated rapid antigen SARS-CoV-2 diagnostic test will be performed locally to confirm eligibility (Table 1). A documented historical positive result from a test conducted ≤ 5 days prior to randomization is acceptable for confirming eligibility.

Samples for the following will be sent to designated central laboratories or Sponsor designee for analysis, on the schedule outlined in Table 1:

- Nasopharyngeal (NP) swab samples for SARS-CoV-2 RT-qPCR; an aliquot will be dedicated for resistance analyses which will be described in a separate resistance monitoring plan. Aliquots may also be analyzed for viral titer and other respiratory pathogens such as influenza and RSV to rule out co-infection
- Blood samples will be collected for potential future biomarker analyses

 others will be kept for future use to potentially analyze disease-related biomarkers or other immune markers to inform the course of the disease.
- Plasma samples for sparse PK analysis

All samples will be processed, stored, and shipped according to the sample processing instructions supplied by the Sponsor or receiving laboratory.

For any subject who experiences a COVID-19 symptom relapse, an NP swab should be collected as soon as possible at the time of symptom relapse. If symptom relapse occurs outside of the planned visit schedule in Table 1, an unscheduled visit should occur to collect the NP swab. Subjects will be instructed to contact their site if they feel their COVID-19 symptom(s) have returned or worsened, after experiencing alleviation or improvement.

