4.5. Clinical Assessments

The following assessments will be performed at Screening, defined as within 24 hours of first dose of study drug, only:

- Demographics
- Medical history and baseline characteristics
- Pre-existing symptoms
- Height and weight
- Complete physical examination

)

- Pregnancy test (females of childbearing potential)
- Rapid test for influenza.

Information on study drug dosing will be collected on Days 1-6 and a plasma sample for evaluation of sparse pharmacokinetics will be collected on Day 5.

The following assessments will be performed at visits corresponding to Days 1, 5, 14 and Early Termination (ET):

- Central safety laboratory values
- Potential blood biomarkers

The following assessments will be collected at each study visit from Day 1 onward (during the 29-day follow-up period i.e., Days 1, 3, 5, 7, 14, 29, and ET if applicable) with exceptions noted:

- Vital signs, to Day 14
- Symptom-targeted physical examination, as clinically indicated
- Nasopharyngeal (NP) swab for central assessment of SARS-CoV-2 virus (quantitative RT-PCR and potential viral titer)
- Adverse events (SAEs out to Day 60)
- Concomitant medications
- Assessment of COVID-19 related medically attended visit(s) (out to Day 60).

Patient reported COVID-19 symptoms will be collected daily on Days 1-29. Symptoms are captured via the COVID-19 symptom diary (see Section 11.1).

At the extended follow-up visit on Day 60, planned collection includes assessment of medically attended visit(s) and serious adverse events.

Version 5 June 24, 2024

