8.5. Multiple Comparisons and Multiplicity

If a statistically significant result is found on the test of the primary endpoint, sequential testing will be performed for the secondary endpoints in the following order. When endpoint is tested for both Day 29 and Day 60, the order will be Day 29 first, followed by D60.

- 1. Proportion of subjects in the supportive-care-only population with all-cause hospitalization or all-cause death through Day 60
- 2. Proportion of subjects in the supportive-care-only population with all-cause hospitalization, all-cause death, or COVID-19 related medically attended visits through Day 29 and Day 60.
- 3. Proportion of subjects in the supportive-care-only population with COVID-19-related hospitalization or who died due to any cause death through Day 29 and Day 60
- 4. Proportion of subjects in the supportive-care-only population who died due to any cause through Day 29 and Day 60
- 5. Proportion of subjects in the supportive-care-only population with COVID-19-related complications (e.g., death, hospitalization, radiologically confirmed pneumonia, acute respiratory failure, sepsis, coagulopathy, pericarditis/myocarditis, cardiac failure) through Day 29 and Day 60
- 6. Proportion of subjects in the supportive-care-only population with COVID-19-related medically attended visits (hospitalization, ER visit, urgent care or physician's office visit or telemedicine visit) or who died due to any cause through Day 29 and Day 60.
- 7. Proportion of subjects in the supportive-care-only population with COVID-19-related medically attended visits through Day 29 and Day 60
- 8. Proportion of subjects in the supportive-care-only population with COVID-19 symptom relapse through Day 29
- 9. Proportion of subjects in the supportive-care-only population with viral load rebound through Day 29
- 10. Proportion of subjects in the combination-antiviral population with COVID-19 symptom relapse through Day 29
- 11. Proportion of subjects in the combination-antiviral population with viral load rebound through Day 29

Version 5 June 24, 2024

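### Viral load rebound counts swabs triggered by symptom relapse, so if BEM lowers relapse the rebound comparison can favour BEM with no true difference in rebound

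*SAP*

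**What the plan says.** - **Definition.** SAP 8.7 counts a rise of at least 1 log10 by RT-qPCR "at any non-missing time point (including unscheduled assessments) after EOT". On who is evaluable it says: "Subjects must have at least one post-EOT measurement result to be evaluated for viral load rebound". One relapse swab could therefore make a subject evaluable.
- **Scheduled swabs.** SAP 4.5 lists visits at "Days 1, 3, 5, 7, 14, 29, and ET if applicable", the same for both arms. After treatment that leaves Days 7, 14 and 29, or early termination.
- **Extra swabs.** Protocol 6.6: "If symptom relapse occurs outside of the planned visit schedule in Table 1, an unscheduled visit should occur to collect the NP swab". Footnote f to Protocol Table 1 agrees: "For subjects with COVID-19 symptom relapse, NP swabs should also be collected at the time of relapse". The documents name no other trigger. The site learns of a relapse from the subject: "Subjects will be instructed to contact their site if they feel their COVID-19 symptom(s) have returned or worsened, after experiencing alleviation or improvement".
- **Testing.** SAP 8.5 places relapse at item 8 and "Proportion of subjects in the supportive-care-only population with viral load rebound" at item 9. Items 10 and 11 repeat the pair in the combination antiviral population. Tests are one-sided at 0.025 (SAP 6.1), with the same stratified comparison as the primary endpoint (SAP 8.7).
- **Checks.** The supplemental analyses in SAP Table 4 concern the primary endpoint only. No analysis of rebound on scheduled swabs alone is planned.

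**The concern.** The chance of finding a rebound depends on how often a subject is swabbed, and that depends partly on relapse. Reducing relapse is one of the effects hoped for from BEM. If BEM does reduce it, placebo subjects will probably have more extra swabs, and more of their between-visit rebounds will be found. Blinding does not prevent this, because the imbalance would follow from a treatment effect on symptoms.

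The stated objective for this endpoint is antiviral activity. At stake is a rebound difference that reflects how often the arms were swabbed rather than what the virus did. The test order adds to this: rebound is formally tested only after relapse has been significantly lower on BEM, which is when the arms are most likely to differ in extra swabs.

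**Working it through.** **1. Figures from the documents.** The SAP's base size is reproduced: 4% v 1.6%, one-sided 0.025 and 90% power give 991 per arm, 1982 in total. Then 1982 × 1.055 = 2091, which the SAP states as 2100, or 1050 per arm. The documents give no planning figure for rebound, so there is none to reproduce. The gaps between scheduled post-treatment swabs are 14 − 7 = 7 days and 29 − 14 = 15 days.

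**2. Assumed inputs (none is in the documents).**
- R: true rebound risk, equal in both arms, 10–15%
- s: share of rebounds seen at scheduled swabs, 0.5–0.7
- c: chance that a relapse swab catches a rebound otherwise missed, 0.8
- l: relapse risk, placebo v BEM, 15% v 10% or 20% v 12%
- k: relapse risk in rebounders relative to overall, 1 to 3
- h: share of relapses that lead to an extra swab, 1 or 0.5

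**3. Formulas.** Let r = h × k × l, the share of rebounders who get an extra swab.
- Detected risk = R × [s + (1 − s) × r × c]
- Spurious difference d = R × (1 − s) × c × (r placebo − r BEM)
- Rejection probability ≈ Φ(d/SE − 1.960), with SE = √[2p̄(1 − p̄)/1050]

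The difference d is zero when relapse is equal in the two arms, and also when unscheduled swabs are not counted.

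**4. Cases at 1050 per arm.**

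| Case | R | s | l | k | h | Detected, placebo v BEM | Ratio | Rejection |
|---|---|---|---|---|---|---|---|---|
| Low corner | 10% | 0.7 | 15% v 10% | 1 | 1 | 7.36% v 7.24% | 0.98 | 0.032 |
| Middle | 10% | 0.6 | 15% v 10% | 2 | 1 | 6.96% v 6.64% | 0.95 | 0.048 |
| High corner | 15% | 0.5 | 20% v 12% | 3 | 1 | 11.10% v 9.66% | 0.87 | 0.190 |
| High corner, half swabbed | 15% | 0.5 | 20% v 12% | 3 | 0.5 | 9.30% v 8.58% | 0.92 | 0.083 |
| Scheduled swabs only | any | any | any | any | – | R × s in both arms | 1.00 | 0.025 |

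High corner in full:
- Placebo: 0.15 × (0.5 + 0.5 × 0.60 × 0.8) = 0.1110
- BEM: 0.15 × (0.5 + 0.5 × 0.36 × 0.8) = 0.0966
- d = 0.0144, SE = √(2 × 0.1038 × 0.8962/1050) = 0.01331
- Φ(1.082 − 1.960) = 0.190

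**5. Given that item 8 is significant.** Simulation over 24 combinations of these inputs (40,000 trials each) gives about 0.03 to 0.19 when every relapse leads to an extra swab, with a median of about 0.06. If half do, it is about 0.03 to 0.08. With scheduled swabs only it is 0.024 to 0.027.

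**6. Combination population.** Up to 300 subjects are planned, so I assume 150 per arm. In the high corner SE = 0.01331 × √(1050/150) = 0.0352, and Φ(0.0144/0.0352 − 1.960) = 0.06. Given a significant relapse result, simulation gives about 0.03 to 0.10. Part of that excess is selection. In small arms a significant relapse result favours trials with a large chance imbalance, which carries over to rebound when the two are correlated. Scheduled-only counting does not remove that part.

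**7. How often item 9 is reached.** Counting Day 29 and Day 60 separately, the tests before item 9 are the primary (1), item 1 (1), items 2–7 (6 × 2 = 12) and item 8 (1). That is 15, and two of them are all-cause death. The documents give no death rate. With an assumed 60% reduction and 1050 per arm, power for Day 29 death alone is 0.11, 0.21, 0.38 and 0.65 at placebo mortality of 0.2%, 0.5%, 1% and 2%.

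**The case against.** **The gate.** A reader might infer that a drug which only reduces symptom relapse could earn a formal rebound claim. SAP 8.5 does not support that. The primary endpoint must succeed first, and such a drug passes it about 2.5% of the time, so its chance of a formal rebound claim is at most about 0.025. The formal risk concerns a drug with real effects on hospitalization or death and on symptoms, but none on rebound. This objection stands. The rates in step 5 of the working are conditional, not overall rates of false claims.

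**Diary and swab are not the same event.** A reader might also infer that placebo must have had more extra swabs whenever rebound is tested. Item 8 is scored from diary question 4 (SAP 8.7), whereas the swab follows contact with the site (Protocol 6.6). A relapse at a planned visit adds no swab, and compliance is unknown. An excess is likely but not certain. The half-swabbed rows reflect this.

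**The inputs are assumed.** This stands too. The low end is close to 0.025. At k = 1 relapse is unrelated to rebound, so an 80% catch rate is hard to justify. If scheduled swabs catch most rebounds, the bias is small.

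**Scheduled-only counting loses information.** It leaves the 15-day gap and drops some symptomatic rebounds. A scheduled-only sensitivity table would be a smaller change. It would expose the problem but leave the alpha-controlled test on the definition that depends on relapse.

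**Conclusion.** The point holds in conditional form. As defined, rebound is detected partly through another endpoint that treatment may change, and no planned analysis shows how much this matters. If BEM lowers relapse, observed rebound can favour BEM although true rebound is equal. If relapse is equal, the test keeps its level.

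The size is uncertain. Under the assumptions above, the spurious risk ratio runs from about 0.98 to 0.87 in the cases shown with every relapse swabbed. The conditional false-positive rate is several times nominal at worst and close to nominal at best.

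The fixed sequence limits formal false claims. It does not protect the rebound proportions that will be reported whether or not item 9 is tested, nor the exploratory relapse-plus-rebound endpoint, which uses the same rebound criterion. The primary analysis and its sample size are unaffected.

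**What to change.** In SAP 8.7:
- Define the tested rebound endpoint (SAP 8.5 items 9 and 11) on scheduled post-treatment swabs at Days 7, 14 and 29, and base evaluability on at least one of them. State how an early-termination swab is treated.
- Identify these swabs by nominal visit, not by the SAP Table 3 windows. Those windows run without a gap from Day 7 to Day 36, so a relapse swab could fill one.
- Report the any-swab version as a labelled supportive analysis, with the number of post-treatment swabs per subject by arm.
- Keep relapse-triggered swabs for the exploratory relapse-plus-rebound endpoint.

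The cost is a short SAP edit and one supportive table, made before unblinding. Swab collection does not change. The downside is that some rebounds between visits are not counted in the tested endpoint, so it has fewer events.

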8.8. Analysis of Exploratory Efficacy Endpoints

The following exploratory endpoints will be examined in both supportive care only and combination antiviral arms.

Time to sustained alleviation or improvement of COVID-19 symptoms

Sustained alleviation/improvement of COVID-19 signs/symptoms is defined as the first occurrence of 4 consecutive days when all symptoms recorded as moderate or severe at study entry are recorded as mild or absent and all symptoms scored mild or absent at study entry are scored as absent. The first day of the 4 consecutive-day period corresponds to the day that the event is achieved. The endpoint will be based on targeted symptoms, which are the 13 symptoms with severities ranging from none to severe in Item 3 of the COVID-19 symptom diary. Subjects who do not achieve the endpoint will be censored according to the following rules:

Case	LOD-3	LOD-2	LOD-1	Last Observed Day (LOD)	Censoring time
1	Not Met	Not Met	Not Met	Not Met	LOD+1
2	Not Met	Not Met	Not Met	Met	LOD
3	Not Met	Not Met	Met	Met	LOD-1
4	Not Met	Met	Met	Met	LOD-2

The cumulative distribution function for time from Day 1 to sustained alleviation/improvement of symptoms will be estimated by Kaplan-Meier methodology and plotted by treatment group. The summary display will include the Kaplan-Meier estimates of proportion achieving the endpoint by day. The analysis will also be carried on subgroups of time from onset of symptoms (<=3 days, > 3days).

Sensitivity analysis will be carried using the same methods for 2 selected subsets of symptoms: 1) runny/stuffy nose, sore throat, cough, feeling hot or feverish, and fatigue; 2) runny/stuffy nose, sore throat, shortness of breath, feeling hot or feverish, headache, and chills; 3) all symptoms from Item 3 of the COVID-19 symptoms diary except fatigue.

Additional subgroup analyses on age group (<65 and >=65), and symptom onset days (<=3 days and >3 days) for time to sustained alleviation of all 13 symptoms will be performed.

Time to self-reported return to usual (pre-COVID-19) health

Self-reported return to usual health is defined as the occurrence of 4 consecutive days when the response to "Have you returned to your usual (pre-COVID) health?" in question 3 of the COVID-19 symptom diary indicates return to usual health. Analysis and data handling will be the same as that described for the endpoint of time to alleviation or improvement of COVID-19 symptoms. The analysis will also be carried on subgroups of time from onset of symptoms (<=3 days, > 3days).

Proportion of subjects requiring post randomization rescue therapy

Post randomization rescue therapies will be identified by blinded medical review. The number and proportion of subjects requiring post randomization rescue therapy will be tabulated.

Duration and severity of COVID-19 symptom relapse

For subjects who meet the criteria of COVID-19 symptom relapse, duration of relapse will be computed by counting the number of days that the relapse question (i.e., question 4 of the COVID-19 symptom diary) is answered "yes". Severity will be based on the average response to question 1 of the COVID-19 symptom diary during the days where relapse is indicated. Subjects with the last record indicating relapse will have duration of relapse right censored. Kaplan-Meier analysis will be used to summarize symptom relapse duration by treatment group. Severity of symptom relapse will be summarized descriptively. The analysis will also be carried on subgroups of time from onset of symptoms (<=3 days, > 3days).

Proportion of subjects with symptom relapse and viral rebound

The proportion of subjects who meet both the symptom relapse and viral rebound criteria will be compared between the BEM and placebo arms using the same method as in the primary analysis. The analysis will also be carried on subgroups of time from onset of symptoms (<=3 days, > 3 days) and baseline viral load groups (<median, >=median).

Time to cessation of SARS-CoV-2 viral shedding by RT-qPCR Time to cessation of SARS-CoV-2 viral shedding will be explored using Kaplan-Meier analysis in two ways: 1) time from first detectable observation of SARS-CoV-2 to the time of the first observation with non-detectable SARS-CoV-2; 2) time from first detectable observation of SARS-CoV-2 to the time of first non-detectable observation of SARS-CoV-2 where the non-detectable status is sustained through Day 29. Where a subject does not meet the cessation endpoint, time to cessation will be censored at the time of the last viral RNA assessment. In cases where the result of SARS-CoV-2 testing is reported as inconclusive, the following rules will be applied:

- If inconclusive observation happens before the first non-detectable observation and all follow up observations are non-detectable, time to sustained cessation is time to the first non-detectable observation.
- If inconclusive observation happens between two non-detectable observations, it is treated the same as non-detectable observation.
- If inconclusive observations happen in the last assessments, time to cessation will be censored at the time of last non-inconclusive assessment.

Change from baseline in amount of severe acute respiratory syndrome coronavirus-2 (SARS-CoV-2) viral RNA as measured by reverse transcription quantitative polymerase chain reaction (RTqPCR) over time and Proportion of subjects negative for SARS-CoV-2 viral RNA by RT-qPCR over time

SARS-CoV-2 viral RNA (and change from baseline) will be summarized at each scheduled time point by descriptive statistics on log_{10} viral load and tabulation of the number and percentage of subjects with non-detectable virus. The analysis will also be carried on subgroups of baseline viral load (<median, >=median).

Area under the curve (AUC) in the amount of SARS-CoV-2 viral RNA as measured by RTqPCR

Area under the log_{10} viral load curve will be computed, out to each of Days 5, 7 and 14, and summarized using descriptive statistics. AUC will be derived using the trapezoidal rule and consider actual study day (per Section 6.7.2) as time. The analysis will also be carried on subgroups of baseline viral load (<median, >=median).

